As discussed above, onabotulinumtoxinA is often used for patients that have failed conservative therapy with medications, pelvic floor physical therapy and/or steroid trigger point injections. However, the optimal dosing and frequency of use has not been determined and needs further study. In addition, the effect of onabotulinumtoxinA injections on the need for additional therapy is unclear but may be beneficial for several reasons. First, if relief is able to be maintained over a longer time period initially, patients may be able to avoid having to undergo repeated TPI over 3 to 5 sessions which can be painful, costly, and time consuming and they may progress to needing onabotulinumtoxinA anyway. Second, by providing more immediate and prolonged relief, requirements for other therapies such as pelvic floor physical therapy and narcotic pain medications may be reduced. Third, because many of our patients with pelvic pain present with high tone pelvic floor dysfunction, we expect global intralevator trigger point injections to be more effective than single site injections. Lastly, we know that chronic pelvic pain is associated with anxiety and depression and we hope that the more immediate and prolonged result of onabotulinumtoxinA will provide patients with improved mental health scores.

Objectives and/or Endpoints

The primary objective of this study is **to assess changes in overall pain score using the visual analog scale (VAS) (Appendix 1), the Brief Pain Inventory (BPI) (Appendix 2) and Global Response Assessment (GRA)(Appendix 3) questionnaire at one month** following transvaginal trigger point injections with a steroid (triamcinolone) and a local anesthetic (ropivacaine) vs. onabotulinumtoxinA and a local anesthetic (ropivacaine) in patients with CPP and high-tone pelvic floor dysfunction. We hypothesize that patients in the Botox group will have lower pain scores following treatment and that the treatment will have a longer effect compared to patients in the Kenalog group.

The secondary objective is to determine if there are persistent changes in pain scores using the VAS, BPI, and GRA at 3 and 6 month follow up. Lastly, patients will be asked to complete a questionnaire to determine what other treatments have been needed since the original TPI (Appendix 4).

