Patients will be asked to refrain from any additional treatments including pelvic floor physical therapy, or new prescriptions for intravaginal muscle relaxants or narcotic medications during the first month following the initial TPI. If patients are already taking muscle relaxants or narcotics, they will need to either remain stable or decrease the dosage and frequency of the medication. If patients are already receiving pelvic floor physical therapy, they may continue treatment. If patients require increased use of these medications or additional therapies due to worsening or uncontrolled symptoms, these treatments will be provided at the discretion of the treating clinician. These patients will then be evaluated as an intention to treat cohort. In addition, at the one month follow-up visit with the clinician, further treatments will be offered based on the patient's need for further symptom control.

We hope that the information obtained by this study will help guide clinicians to make an evidenced based decision on the clinical efficacy as well as cost effectiveness of two transvaginal trigger point injection protocols for patients with high-tone pelvic floor dysfunction.

Methodology

A randomized, double blind two arm study. Up to 40 women will be included to complete this study. We may enroll up to 60 patients to account for possible dropouts, with each arm having up to 20 subjects. This is a pilot trial and a formal sample size has not been completed. Subjects will be recruited by physician referral or word of mouth. Study activities will take place at the Women's Urology Center in the south tower of Beaumont Hospital, Royal Oak.

Screening

Subjects are eligible to participate in this study if they are a woman greater than 18 years old and have pain localized to the pelvis for greater than 3 months. Overall pelvic pain score must be greater than 4 on the VAS. They will be screened with assessment of last menstrual period (LMP) and a urine pregnancy test. If the woman has had a tubal ligation or a hysterectomy, the pregnancy test will be waived.

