Subjects may be permitted to withdraw from the study if they have poor resolution of their pain or worsening of their symptoms. If they feel that they need other therapy during the first 30 days that is not permitted by the study (additional physical therapy, higher or more frequent doses of vaginal valium or pain medications, repeat TPI, etc.) they may be withdrawn and will be evaluated by the clinician for other treatment options. Patients who withdraw from the study will be asked if they are willing to fill out post questionnaires. Either group can get additional therapy following the first 30 days following the TPI. Furthermore, either group may have repeat TPI with kenalog one month following the original injection but patients may not undergo TPI with onabotulinumtoxinA following the original injection unless they withdraw from the study and are unblinded to prevent overdose of onabotulinumtoxinA. If additional TPIs with kenalog and ropivicaine are indicated at any of the follow up visits, the injections will be prepared and administered in the Woman's Urology Center, per routine standard of care. In no way will their withdrawal from the study impact what treatments will be offered to them. Subjects may also withdraw from the study without any reason given. If they do not feel comfortable continuing treatment by the study clinicians or at the WUC, they will be referred to another provider/site not involved in the study.

Schedule of Activities

| | Initial Visit | Treatment Visit | 30 days | 90 days | 180 days |
|--|----------------------|--|----------------------------|----------------------------|----------------------------|
| | Screening Consent | Baseline Questionnaires and physical exam (May be done at initial visit) | | | |
| Screening | x | | | | |
| Consent | X | | | | |
| Intake medical history form | X | X (If not done at initial visit) | | | |
| Urine pregnancy test ^a | x | | | | |
| Q tip test | X | X | Xp | Xp | Xp |
| Vaginal pH and wet mount | X | X (As needed) | X ^b (As needed) | X ^b (As needed) | X ^b (As needed) |
| Assess concomitant meds | X | X | Х | X | X |
| Vaginal exam assessment for high tone pelvic floor dysfunction with record of patient reported levator pain scores | X | X | Xp | Xp | Xb |
| Vital signs | X | X | Xb | Xb | Xp |
| Total overall pelvic pain score on VAS | x | X (done pre and post TPI) | X | x | X |
| BPI | | X | x | X | X |
| Trigger point injection | | X | As needed | As needed | As needed |

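### The 3- and 6-month change scores are not linked to re-treatment woman by woman, so on their own they cannot show whether relief from the original injection persists or lasts longer with onabotulinumtoxinA

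*Protocol*

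**What the plan says.** **The question.** Protocol, Objectives and/or Endpoints: "The secondary objective is to determine if there are persistent changes in pain scores" at 3 and 6 months, measured by VAS, BPI and GRA. The same section hypothesises that the effect lasts longer with onabotulinumtoxinA than with Kenalog.

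**What is allowed after one month.** Extra treatment is restricted only in the first month. At the 30-day contact, "at the one month follow-up visit with the clinician, further treatments will be offered based on" the need for symptom control. The withdrawal text before the Schedule of Activities adds: "Either group can get additional therapy following the first 30 days following the TPI", and "either group may have repeat TPI with kenalog one month following the original injection". The Schedule lists trigger point injection (TPI) as needed at 30, 90 and 180 days. Repeat onabotulinumtoxinA requires withdrawal and unblinding.

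**What is recorded.** A questionnaire at 90 and 180 days asks about other treatments since the original injection, and concomitant treatments are assessed at every follow-up visit.

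**What is analysed.** Protocol, Data Analysis, describes pain scores only at treatment and 30 days. The SAP calculates each woman's change from baseline to one, three and six months, promises descriptive statistics for all variables, and runs no tests at 3 and 6 months because 23.8% of the sample was missing. Neither document relates a later score to whether that woman had been re-treated.

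**The concern.** Re-treatment depends on symptoms and comes before the very scores that are meant to show persistence. A woman whose first injection has worn off can be re-injected with Kenalog, improve, and enter the 3-month summary looking like a woman whose first injection is still working.

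This bears on the trial's own rationale. The Background describes a comparison in other muscles in which the two treatments were similar at 30 days and onabotulinumtoxinA was better at 60 days. It also argues that longer relief might spare women repeated injections. The expected contrast thus falls in the period when re-treatment opens, and no planned summary shows improvement kept without it.

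**Working it through.** **1. Can re-treatment precede the later scores?** Visit windows from the protocol: 30 ± 7 days (day 23 to 37), 90 ± 30 (day 60 to 120), 180 ± 30 (day 150 to 210).
- Injection at the 30-day visit to the 3-month score: 60 − 37 = 23 days, up to 120 − 23 = 97 days.
- Injection at the 90-day visit to the 6-month score: 150 − 120 = 30 days, up to 210 − 60 = 150 days.

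So yes, by weeks to months.

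**2. Do the planned scores tell the cases apart?** Take two women, each 1 VAS point better at day 30. One is re-injected that day and the other is not. Both are 3 points better at day 90. Their change scores are −1 and −3 in both cases. Only the treatment record separates them, and the plan does not join it to the scores.

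**3. How many women?** With enrolment capped at 60 ("We may enroll up to 60 patients to account for possible dropouts"), 23.8% can only be 5/21 or 10/42. Taking 42, split evenly (assumed): 42 − 10 = 32, or 16 per arm.

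**4. Shift in a difference of means.** Shift = (extra women re-injected in one arm) × g / n, in that arm's favour. Here n = 16, and g, the gain from a repeat injection, is assumed to be 1 to 3 points. As a guide to g, the steroid series in the Background had 13 of 18 women with a fall of at least 50%, 6 of them pain free. At the entry VAS of 4, with no change in the other 5, the mean fall is at least (6×4 + 7×2 + 5×0)/18 = 38/18 = 2.1. Whether a repeat injection does as well is not known.

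| Extra women re-injected | g = 1 | g = 2.1 | g = 3 |
|---|---|---|---|
| 1 | 0.06 | 0.13 | 0.19 |
| 4 | 0.25 | 0.53 | 0.75 |
| 8 | 0.50 | 1.06 | 1.50 |

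With 21 women (8 per arm left) each shift doubles. With equal numbers and equal gain the difference does not move, but both arms look more persistent than they are. For example, take assumed true changes of −1 (Kenalog) and −3 (onabotulinumtoxinA), half of each arm re-treated and g = 2: the observed changes are −2 and −4.

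**5. Medians.** The SAP allows mean or median, and step 4 does not carry over to medians. In a simulation of 16 women (assumed change scores with mean −2 and SD 2.5, rounded, the worst-off re-injected), one re-injection left the median unchanged in 91 to 100% of runs for g = 1 to 3. Four left it unchanged in about 96% (g = 1), 65% (g = 2) and 30% (g = 3).

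**6. Precision of a re-treatment-free proportion.** Counts are invented for illustration; intervals are Newcombe 95%.
- 9/16 v 5/16: 25 points (−9 to 52), if 5 lost women per arm are left out.
- 9/21 v 5/21: 19 points (−9 to 44), if all 5 per arm count as not improved.

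The withdrawal rule therefore changes the figure even when it is the same in both arms, so it should be written down.

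**The case against.** **Re-treatment is already an outcome.** The protocol pairs the later scores with a questionnaire on other treatments, and the SAP describes all variables. This stands: counts by arm may well be reported, and scores plus counts are a legitimate description of a treatment strategy. But two separate tables do not show which improved women were re-injected.

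**The documents do not define persistence as relief without re-treatment.** True for the secondary objective as worded. The longer-effect hypothesis, however, is about duration, and scores that mix in later injections do not answer it.

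**Intention to treat covers it.** "These patients will then be evaluated as an intention to treat cohort" follows the rules on extra treatment in the first month. Carried forward, it would keep re-treated women in the summary without showing whose relief came unaided.

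**A re-treatment-free outcome has faults of its own.** This stands. It combines initial response with duration. Requiring improvement at one month as well would score late responders as failures, although the Background gives reason to expect some. And since the Background says a course typically takes 3 to 5 injections, a repeat injection may be the usual course and not loss of effect.

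**Readings that go too far.** A reader might infer that the 3- and 6-month summaries are invalid, that re-treatment must hide an onabotulinumtoxinA advantage, or that the main result is at risk. The documents support none of these. The summaries validly describe injection plus later care. No re-treatment rates are given, so no direction can be claimed. Repeat injection opens only at one month, so the primary comparison is largely unaffected.

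**Conclusion.** The point holds as a gap in the planned analysis, not in data capture. The later change scores cannot by themselves show that the original injection's effect persists, or that it lasts longer in one arm. Size and direction are unknown. The 0.06 to 1.5 point range applies only to differences in means, with an assumed 16 women per arm, a gain of 1 to 3 points, and 1 to 8 extra women re-injected in one arm; medians may not move when few are re-injected. The consequence is modest: this is an exploratory pilot, no tests are run at 3 or 6 months, and only descriptive secondary results are touched. It is an improvement worth making because it is cheap and addresses a question the protocol itself asks.

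**What to change.** Add to the SAP, marked as added and exploratory:

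1. Keep the 3- and 6-month summaries and label them as original injection plus later treatment.
2. By arm and visit, report the number of women with a repeat TPI before that score, and show the scores split by repeat TPI yes or no. State that the split is descriptive, because re-treatment is chosen after randomisation.
3. By arm, with a 95% interval, report the proportion of all randomised women with known status who are improved from baseline on the VAS at that visit with no repeat TPI before it. Do not require improvement at one month, so that late responders count; a version that does may be shown as secondary. Use one withdrawal rule in both arms. The protocol says "Subjects may be permitted to withdraw from the study if they have poor resolution of their pain or worsening of their symptoms"; such withdrawals, and withdrawals to receive onabotulinumtoxinA, count as not improved. It also says "Subjects may also withdraw from the study without any reason given"; these and any other unknown status are shown as missing, by arm.
4. Add a sensitivity version that also counts new or increased pelvic pain therapy (physical therapy or medication) as not improved.

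**Cost.** SAP wording and a few descriptive rows, with no change to care or to the one-month analysis. Treatments are already recorded for each woman, and repeat Kenalog at follow-up visits is given in the study clinic. Withdrawal reasons must come from study records.

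**Downsides to state.** A yes/no outcome is coarse and its intervals will be wide. It does not isolate duration from initial response. A repeat injection may be part of a usual course. The SAP is written in the past tense, so the addition is post hoc.

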A DOUBLE-BLIND, RANDOMIZED STUDY TO COMPARE ONOBOTULIUMTOXIN A VERSUS KENALOG FOR INTRAVAGINAL TRIGGER POINT INJECTIONS IN THE TREATMENT OF CHRONIC PELVIC PAIN

Principal Investigator: [name], DO

Version Date: August 23, 2017

Study Overview

Background

Chronic pelvic pain (CPP) is a common and often debilitating problem among women. A practical clinical definition of CPP is non-cyclical pelvic pain that is of at least 6 months duration¹. CPP occurs below the umbilicus and is severe enough to cause functional impairment or require treatment. CPP affects approximately 15% of women and the health care burden is substantial. The direct cost of physician/clinician visits is estimated to be over \$880 million and the indirect costs due to lost work is estimated at \$555 million².

Patients with CPP often go undiagnosed for years and see many different healthcare providers before getting the correct diagnosis and subsequent improvement in their symptoms^{3, 4}. Depending on the treating specialists, patients may be diagnosed with bladder pain syndrome/interstitial cystitis (BPS/IC), endometriosis, vulvodynia, or irritable bowel syndrome. A definitive diagnosis may be lacking in up to 60% of patients seeking treatment for CPP⁵. Patients with CPP report that their quality of life is diminished and their relationships with loved ones are often damaged^{6, 7}. They may have lost their job as a result of missed work days or inability to function appropriately due to pelvic pain symptoms.

The musculoskeletal system is an important factor in chronic pelvic pain, specifically the persistent and refractory type⁸. Myofascial pain and hypertonic pelvic floor dysfunction are present in as many as 85% of patients with bladder pain syndrome/interstitial cystitis and/or chronic pelvic pain syndromes⁹. The pelvic floor muscles are arranged in deep and superficial layers and act as a sling to support the pelvic organs and the bones and ligaments of the pelvis provide support to the pelvic muscles. The deep levator ani muscles, often referred to as the pelvic diaphragm, are the most important of the pelvic floor muscles and consist of the pubcoccygeus, iliococcygeus, and the coccygeus. The main function of the muscles are to control continence and both bowel and urine elimination.

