- Local anesthetic toxicity (numbing medication could be absorbed through the bloodstream into the rest of the body affecting your breathing, heartbeat, blood pressure)

There is a risk of an allergic reaction from any medication. Symptoms may include swelling, skin rash and/or headache, difficulty swallowing or talking, trouble breathing, muscle weakness. Symptoms can occur days to weeks after injection. There may be unknown side effects or problems that could result in serious illness or even death.

Inclusion Criteria

- Provide informed consent
- Healthy women \geq age 18 regardless of menopausal status
- Willing and able to fill out study questionnaires. In patients that are unable to read, the research nurse will be available to assist.
- High-tone pelvic floor dysfunction on vaginal exam
- A pelvic pain score of ≥ 4 on screening VAS
- Pain perceived to be in the pelvis that has been present for at least 3 months.

Exclusion Criteria

- Patients that have had Botox to the bladder within the last 8 months
- Patients that have had Botox outside the bladder of ≥ 160 u within the last 12 weeks.
- Patients that have had transvaginal trigger point injections of any form (Botox or steroid) in the last 3 months
- Pregnancy
- Concomitant use of any narcotic drug, alcohol, or any illicit drug use during the study period that could be deemed unsafe in combination with study medication as judged by the investigators.
- Any evidence of vaginitis on wet mount slide at initial visit that is untreated.
- Subject with any other vaginal epithelial disorder that could affect absorption of medication as deemed by the investigators.

Page **10** of **14**

- Any indication/condition/medication that the investigators identify as contraindicated in conjunction with study medication.
- Systolic blood pressure > 160 mm Hg on screening blood pressure
- Heart rate > 110 beats/minute on screening heart rate

Randomization

Subjects will be randomized to one of the two trigger point injection types by a sealed randomization envelopes (or similar randomization) created by our biostatistician. Patients will be randomized in a 1:1 pattern in varied randomized block design.

Recruitment

We anticipate recruitment will come from volunteers with pelvic pain both within and outside the Beaumont health care system urology and gynecology practices by physician referral and word of mouth.

Data Analysis

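### The safeguard against onabotulinumtoxinA overdose after the blinded injection covers trigger point injection only, not the drug by other routes

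*Protocol*

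**What the plan says.** The rule stands in the protocol's text on withdrawal and additional treatment, just before the Schedule of Activities: "patients may not undergo TPI with onabotulinumtoxinA following the original injection unless they withdraw from the study and are unblinded to prevent overdose". The same paragraph says "Either group can get additional therapy following the first 30 days following the TPI" and lets either group have a repeat steroid TPI from one month.

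The Exclusion Criteria look back at earlier toxin by route. They exclude "Patients that have had Botox to the bladder within the last 8 months". For other sites the criterion adds a dose threshold and sets a shorter interval: "Patients that have had Botox outside the bladder of ≥ 160 u within the last 12 weeks". A transvaginal TPI of either kind in the previous 3 months also bars entry. No reasons are given for these intervals.

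Under Proposed intervention, Group 2 receives 200 u of onabotulinumtoxinA in the pelvic floor and Group 1 receives none, with both groups' syringes darkened to keep the blind.

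**The concern.** Overdose depends on the drug and on total exposure, but the check depends on the type of procedure. A clinician who considers bladder or other-site onabotulinumtoxinA after day 30 would not know whether the woman already holds 0 or 200 u, and nothing visible tells that clinician to find out first. For TPI, the protocol did not rely on clinicians assuming 200 u. It required withdrawal and unblinding.

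The matter is one of safety. The Risks section lists transient urinary retention (1% to 10%) and toxicity or intolerance (under 1%) among the toxin's risks. The trial's results are hardly touched. The primary time point is one month, and patients are asked to avoid additional treatments until then. The SAP reports no tests at 3 and 6 months.

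**Working it through.** The plan gives no figure to reproduce. The check is a comparison of texts, followed by simple arithmetic on the protocol's own intervals.

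**1. Entry rules beside post-dose rules**

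| Route | Earlier dose that bars entry | Rule after the study injection |
|---|---|---|
| Toxin as transvaginal TPI | Any dose, 3 months | Barred unless withdrawn and unblinded |
| Toxin to the bladder | Any dose, 8 months | None visible |
| Toxin to other sites | 160 u or more, 12 weeks | None visible |

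**2. Does other text close the gap?**

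- The request in Objectives and/or Endpoints to avoid additional treatments covers the first month only. It mentions neither onabotulinumtoxinA nor unblinding.
- The clause on contraindicated conditions and medications is an exclusion criterion applied at entry.
- Concomitant medications and treatments are assessed at visits, which records what has already been given. It is not a check before an injection.
- The SAP is silent.

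**3. Which interval fits the study dose?** Each entry interval is set by the site of the *earlier* dose. After randomization the earlier dose is the study dose: 200 u, outside the bladder, given as TPI. Since 200 > 160, the 12-week criterion matches. The 3-month TPI criterion matches too. I assume that the interval applies whatever site is injected next; the protocol does not say so.

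**4. Length of the window**, with the study injection on day 0 and additional therapy open from day 31:

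- 12 weeks: 12 × 7 = 84, and 84 − 31 + 1 = **54 days**.
- 3 months taken as 90 days: 90 − 31 + 1 = **60 days**.
- Earliest exit visit: 180 − 30 = day 150. Both windows close before it, so they lie within follow-up.

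**5. Women concerned**, at 1:1 allocation: 40 / 2 = **20** in the toxin arm, or 60 / 2 = **30** if all 60 are enrolled. These are the women who could hold a blinded 200 u dose. How many of them would be offered other toxin cannot be derived from the documents.

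**The case against.** The strongest reply is that the scenario is unlikely and largely guarded against in practice. Study clinicians know that any participant may hold 200 u. They start further treatment themselves from the 30-day visit and review concomitant treatments at each visit. Investigators can also exclude at entry a woman whose other indications worry them. By excluding other-site Botox only from 160 u, the protocol accepts some combined exposure. The consent pages and Appendix 4 are not available, so patients may have been told to report any Botox. All of this stands and lowers the likelihood, but none of it triggers the check.

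The case that outside clinicians might give the toxin is moderate. The Background says that these patients "see many different healthcare providers before getting the correct diagnosis", but that describes the time before diagnosis, and enrolled women have already been diagnosed. More to the point, recruitment draws on "volunteers with pelvic pain both within and outside the Beaumont health care system urology and gynecology practices", and women not comfortable continuing with the study clinicians are told that "they will be referred to another provider/site not involved in the study". A protocol sentence does not bind those clinicians; an instruction to the patient can reach them.

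A reader might infer a longer exposure by applying the 8-month bladder interval to any later bladder injection, which would run past study exit. The documents do not support this, because the 8 months attach to an earlier bladder dose and the study dose is not one. A reader might also take the listed retention rates as the harm from this gap. Those rates describe the toxin itself and would apply to the study dose whether or not the rule were widened.

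**Conclusion.** The point holds as a minor safety correction: a rule whose declared purpose is to prevent overdose is narrower than that purpose. The clearest exposed window is 54 days, or about 60 on the TPI interval, for up to 20 women (30 if 60 enrol).

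This rests on three assumptions. The entry intervals are a fair guide to how long the study dose counts as recent. They apply whatever the next site. The unseen consent text does not already cover the matter.

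It would go too far to conclude that the protocol authorises such injections or that any woman was overdosed. The protocol does not expressly permit them, and the documents give no cumulative dose limit, no frequency of non-study Botox and no figure for combined exposure. The SAP, dated December 2018, is in the past tense and reports dropout, which suggests that follow-up is complete. In that case the correction is for a successor protocol.

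**What to change.** In the withdrawal and additional-treatment text, replace the words that limit the rule to TPI, so that it bars *onabotulinumtoxinA by any route and at any dose*. Keep the existing condition of both withdrawal and unblinding during follow-up. Do not put a 160 u threshold on the new dose: a smaller dose could then follow a blinded 200 u with no check.

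If the consent form does not already say so, ask patients to tell any outside clinician that they may have received 200 u, and to contact the study team before any Botox.

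The cost is one changed phrase and one instruction, with no new form or visit. A few women may be unblinded or withdrawn, which affects essentially only the untested 3- and 6-month scores. The exception in principle is a woman seen late for the 30-day visit (window ± 7 days, so day 31 to 37). The protocol already accepts this loss for TPI, and it softens it: "Patients who withdraw from the study will be asked if they are willing to fill out post questionnaires".
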